10.2 Analytic Plan

For the phase I study, we will examine three doses, with the first cohort assigned to 20 mg orally daily dose. The MTD will be defined via the 3+3 algorithm, i.e. as the dose level below the one at which 1/3 or 2/6 patients experience DLTs. At the completion of the phase II section, the ORR will be estimated as the proportion of patients with ORR and will be accompanied by a 95% confidence interval.

All observed toxicities will be tabulated by type and grade. All remaining secondary aims will be assessed with descriptive statistics and graphical displays to evaluate changes in outlined serum and bone marrow markers between pre- and post-treatment. A paired t-test will be used to examine differences pre- and post-treatment.

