10.4 Stopping Rules

A response rate of 5% or less will be considered as clinically insignificant, while a response rate of 25% will be considered as clinically significant. With alpha= 0.05 and power of 0.80, the Simon optimal 2-stage design requires minimum enrollment of 9 patients in the first stage. The hypothesis will be rejected and enrollment will cease if no response is seen in the 9 patients. If at least 1 response is seen in the first 9 patients, another 14 patients will be accrued, for a total of 17 evaluable patients. At the end of the trial, the drug will be rejected if no more than 2 responses are seen in the total of 17 evaluable patients.

Cabozantinib will be taken in 20-mg capsules to reach the target dose levels as determined during the phase I and phase II portions of the study. This therapy will be continued without a cap on the number of allowed cycles, unless one of the following occurs:

- ❖ Disease progression after two cycles or later of therapy
- ❖ Intercurrent illness that prevents further administration of treatment
- ❖ Unacceptable adverse event(s)
- ❖ Patient decides to withdraw from the study
- ❖ General or specific changes in the patient's condition render the patient unacceptable for further treatment in the judgment of the investigator
- ❖ Patient becomes pregnant
- ❖ Patient loses the ability to freely provide consent through imprisonment or involuntary incarceration for treatment of a psychiatric or physical illness
- ❖ Patient achieves complete remission (CR), and the patient and investigator feel that discontinuation of cabozantinib is in the patient's best interests, or

- ❖ Patient achieves a level of response that qualifies him or her for another therapy, such as high dose therapy with autologous stem cell transplantation.

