10.7.2 EVALUATION OF RESPONSE

All patients included in the study must be assessed for response to treatment, even if there are major protocol treatment deviations or if they are ineligible. Each patient will be assigned one of the following categories: 1) complete response, 2) partial response, 3) stable disease, 4) progressive disease, 5) early death from malignant disease, 6) early death from toxicity, 7) early death because of other cause, or 9) unknown (not assessable, insufficient data). [Note: By arbitrary convention, category 9 usually designates the “unknown” status of any type of data in a clinical database.]

All of the patients who met the eligibility criteria (with the possible exception of those who received no study medication) should be included in the main analysis of the response rate. Those patients who do not receive a single dose of the investigational drug will be replaced in this trial with new patients. Patients in response categories 4-9 should be considered to have a treatment failure (disease progression). Thus, an incorrect treatment schedule or drug administration does not result in exclusion from the analysis of the response rate.

All conclusions should be based on all eligible patients. Subanalyses may then be performed on the basis of a subset of patients, excluding those for whom major protocol deviations have been identified (e.g., early death due to other reasons, early discontinuation of treatment, major protocol violations, etc.). However, these subanalyses may not serve as the basis for drawing conclusions concerning treatment efficacy, and the reasons for excluding patients from the analysis should be clearly reported. The 95% confidence intervals should also be provided.

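### Section 10.2 reports ORR as a plain proportion with an unspecified 95% CI, not linked to the two-stage design; at 3/17 an exact or Wald interval still contains the 5% rate that the count rule rejects

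*Combined protocol and SAP*

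**What the plan says.** Section 10.2 (Analytic Plan) gives the whole estimation plan for the response endpoint in one sentence: "the ORR will be estimated as the proportion of patients with ORR and will be accompanied by a 95% confidence interval". Section 10.7.2 repeats the level: "The 95% confidence intervals should also be provided". Neither place names an interval method, and neither mentions the two-stage design.

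The decision is defined separately, in sections 10.1 and 10.4. The hypotheses are 5% against 25%, with alpha 0.05 and power 0.80. On the null, section 10.4 says "A response rate of 5% or less will be considered as clinically insignificant". On the design it says "the Simon optimal 2-stage design requires minimum enrollment of 9 patients in the first stage". The stage 1 rule is that "enrollment will cease if no response is seen in the 9 patients", and at the end "the drug will be rejected if no more than 2 responses are seen in the total of 17 evaluable patients". Success therefore starts at 3/17.

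Section 10.4 also says "another 14 patients will be accrued, for a total of 17 evaluable patients", and section 10.1 has the same numbers. Nine plus 14 is 23, not 17.

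**The concern.** ORR is one of the two primary objectives. The estimate and interval will be the most quoted efficacy result, yet they are planned as if the sample were a single fixed group.

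- **Estimate.** Stopping at 0/9 records a zero and removes the chance of stage 2 responses. Averaged over all outcomes, the raw proportion therefore falls below the true rate.
- **Interval.** A two-sided 95% interval leaves 2.5% in each tail, while the design spends 5% in one tail. At the smallest successful result the two can disagree: the report would declare activity and print an interval containing the rate that the plan calls clinically insignificant.

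Because no method is named, whether that happens depends on a choice that could be made after the data are seen.

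**Working it through.** **Inputs.** From sections 10.1 and 10.4: p0 = 0.05, p1 = 0.25, alpha = 0.05, power = 0.80, n1 = 9, stop at 0 responses, total n = 17, drug rejected at 2 or fewer. Assumption: stage 2 has 17 − 9 = 8 patients.

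**1. Reproduce the design.** Let X be responses among the first 9 and Y among the next 8. Success requires X ≥ 1 and X + Y ≥ 3:

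P(success) = P(X=1)·P(Y≥2) + P(X=2)·P(Y≥1) + P(X≥3)

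- At 5%: 0.2985 × 0.0572 + 0.0629 × 0.3366 + 0.0084 = 0.0466.
- At 25%: 0.2253 × 0.6329 + 0.3003 × 0.8999 + 0.3993 = 0.812.

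A full search for the smallest expected sample size under the null returns the same design: 0/9, then 2/17. The stated alpha is met in one tail. The documents do not use the word one-sided; this result and the one-directional null imply it.

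**2. Bias of the plain proportion.** It equals 0 if X = 0 and (X + Y)/17 otherwise. Its expectation is p − (8/17)·p·(1 − p)^9, so the bias is −(8/17)·p·(1 − p)^9.

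| True ORR | (1 − p)^9 | Bias |
|---|---|---|
| 5% | 0.630 | −1.5 points |
| 10% | 0.387 | −1.8 points |
| 25% | 0.075 | −0.9 points |

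**3. Unbiased estimate at 3/17.** With s = 3 total responses and x = 1, 2, 3 in stage 1:

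UMVUE = Σ C(8, x−1)·C(8, 3−x) / Σ C(9, x)·C(8, 3−x) = (28 + 64 + 28)/(252 + 288 + 84) = 120/624 = 19.2%, against a raw 3/17 = 17.6%.

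**4. Intervals at 3/17.**

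| Method | Level | Interval | Contains 5%? |
|---|---|---|---|
| Clopper-Pearson | 95% | 3.8% to 43.4% | yes |
| Wald (truncated at 0) | 95% | 0% to 35.8% | yes |
| Wilson | 95% | 6.2% to 41.0% | no |
| Jeffreys | 95% | 5.2% to 40.0% | no |
| Agresti-Coull | 95% | 5.4% to 41.8% | no |
| Stage-wise exact | 95% | 3.9% to 44.0% | yes |
| Clopper-Pearson | 90% | 4.99% to 39.6% | yes, just |
| Stage-wise exact | 90% | 5.1% to 40.1% | no |

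The stage-wise interval inverts the two-stage tail probabilities, with early stopping ordered lowest. For example, its 90% lower limit is the p at which P(success) = 0.05, which is 5.14%. Among exact intervals, the stage adjustment alone and the 90% level alone both leave 5% inside; together they exclude it.

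**5. Agreement with the rule on both sides of the boundary.** The two-stage p-value at 3/17 is 0.0466. At 2/17, add P(exactly 2) = 108 × 0.05² × 0.95^15 = 0.125, which gives 0.172. The stage-wise 90% lower limit is therefore above 5% at 3/17 and below it at 2/17, as the count rule requires.

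**6. Reach.** At 4/17 Clopper-Pearson 95% is 6.8% to 49.9% and excludes 5%, so with exact intervals only 3/17 is affected. (Wald still contains 5% at 4/17, with a lower limit of 3.4%.) P(exactly 3/17) = 624·p³·(1 − p)^14, which is 0.174 at 25%. Divided by the power, 0.174/0.812 = 21% of successful trials at that rate.

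**The case against.** The strongest reply is that nothing here can change the trial's conclusion. The decision is set by the response count, and the documents never require the interval to exclude 5%. A 95% interval beside a one-sided 5% rule is common practice. All of that stands.

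Three further points also stand:

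- A reader might infer that the planned interval is bound to contradict the decision at 3/17. The documents do not support that. They name no method, and three standard 95% intervals exclude 5%.
- A reader might also infer that a conventional interval is mis-sized because it ignores the two stages. That does not follow either. At 3/17 the exact 95% limits move only from 3.8% and 43.4% to 3.9% and 44.0% once the stages are taken into account. The disagreement comes mainly from the level.
- The bias is small beside an interval about 40 points wide, and it is an average over all outcomes. Among trials that reach stage 2 the raw proportion is biased upward: at 25%, 0.2412/0.9249 − 0.25 = +1.1 points.

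What the reply does not answer is the missing method. If some usual intervals contain 5% at the boundary and others do not, the choice should be fixed before the data are seen. The stated estimator can also be improved at almost no cost.

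**Conclusion.** The point holds as a reporting and interpretation gap in a primary endpoint, worth correcting but not a threat to the design. The 0/9, 2/17 rule is sound as a one-sided 5% test (alpha 0.0466, power 0.812), and the go/no-go decision is untouched.

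The plain proportion is biased low by 0.9 to 1.8 points at the rates tabulated. With an exact 95% interval, one result (3/17, probability about 17% at a true ORR of 25%) would be declared a success while its interval contains 5%.

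This rests on three conditions: one-sidedness is inferred, not stated; the interval method is open; and stage 2 has 8 patients. If 14 were added and the same cut-off applied to 23, alpha would be 0.086. The stage-wise 90% interval at 3/23 would be 4.0% to 32.8%, which contains 5%. The denominator therefore has to be settled before any matched interval can be defined.

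**What to change.** First reconcile the 14 additional patients with the total of 17 in sections 10.1 and 10.4. Then, for a 17-patient design, amend section 10.2 to:

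- report the UMVUE of ORR alongside the response count and denominator;
- give a two-sided 90% interval by stage-wise ordering, equivalently a one-sided 95% lower bound, as the interval matched to the decision;
- keep a Clopper-Pearson 95% interval, labelled descriptive, which also meets section 10.7.2;
- state that the test is one-sided at 5% and that the response-count rule governs the decision.

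The cost is a few sentences, a few lines of code and no patients. There are two drawbacks. Readers will see two intervals and need to be told which one matches the decision. The UMVUE also has a higher root mean squared error than the raw proportion at low true rates (by enumeration, 6.8 against 5.6 points at 5% and 8.8 against 8.4 at 10%). The order reverses from 15% upward (11.3 against 11.8 at 25%).

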10.3 ACCRUAL

Total accrual targets for this study are 32 with flexibility based on enrollment in phase I of the study. This study is planned as a 2-institution study, University of Nebraska Medical Center being the lead site, and MD Anderson Cancer Center a secondary site. Based on prior phase I and II studies at both sites, in a similar patient population, we estimate that 3 patients will be accrued every two months, suggesting that a total of 12-18 months will be needed to meet the sample size.

10.4 Stopping Rules

A response rate of 5% or less will be considered as clinically insignificant, while a response rate of 25% will be considered as clinically significant. With alpha= 0.05 and power of 0.80, the Simon optimal 2-stage design requires minimum enrollment of 9 patients in the first stage. The hypothesis will be rejected and enrollment will cease if no response is seen in the 9 patients. If at least 1 response is seen in the first 9 patients, another 14 patients will be accrued, for a total of 17 evaluable patients. At the end of the trial, the drug will be rejected if no more than 2 responses are seen in the total of 17 evaluable patients.

Cabozantinib will be taken in 20-mg capsules to reach the target dose levels as determined during the phase I and phase II portions of the study. This therapy will be continued without a cap on the number of allowed cycles, unless one of the following occurs:

- ❖ Disease progression after two cycles or later of therapy
- ❖ Intercurrent illness that prevents further administration of treatment
- ❖ Unacceptable adverse event(s)
- ❖ Patient decides to withdraw from the study
- ❖ General or specific changes in the patient's condition render the patient unacceptable for further treatment in the judgment of the investigator
- ❖ Patient becomes pregnant
- ❖ Patient loses the ability to freely provide consent through imprisonment or involuntary incarceration for treatment of a psychiatric or physical illness
- ❖ Patient achieves complete remission (CR), and the patient and investigator feel that discontinuation of cabozantinib is in the patient's best interests, or

- ❖ Patient achieves a level of response that qualifies him or her for another therapy, such as high dose therapy with autologous stem cell transplantation.

10.5 ANALYSIS OF GENE EXPRESSION PROFILING

Our central hypothesis for the correlative laboratory studies is that inhibition of c-Met with cabozantinib will show anti-tumor efficacy especially in patients who have greater activation of the MU20/c-Met pathway at baseline, as determined by genomic and flow cytometry approaches.

10.5.1 DATA PREPROCESSING

For gene expression data, we will apply appropriate normalization methods for the expression profiles, which include quantile normalization⁷⁷ and locally weighted scatterplot smoothing⁷⁸, in order to make analyses comparable across arrays. We shall use robust quantification methods such as the robust multichip analysis⁷⁹ to produce a set of expression measurements, which will be used for subsequent downstream statistical analysis.

10.5.2 DATA ANALYSIS

To assess differential expression, we will use t-tests or Mann-Whitney tests if appropriate. When there are more than two groups, an ANOVA (or non-parametric Kruskall-Wallis ANOVA) model will be used to test for biomarker expression differences among groups. The significance threshold will be chosen based on standard methods that have been developed to adjust for multiple testing for such univariate tests; for example, bounding the false discovery rate (FDR)⁸⁰ using either Significance Analysis of Microarrays (SAM)⁸¹ or Beta-Uniform Mixture (BUM)⁸² models.

10.5.3 PATHWAY ANALYSIS

The candidate signatures identified in the analysis associated with treatment/disease groups will be uploaded into the Ingenuity Pathway Analysis Application (IPA) for pathway analysis. Ingenuity's knowledge base is a repository of molecular interactions, regulatory events, gene-to-phenotype associations, and chemical knowledge that provides the building blocks for pathway construction. The pathways associated with treatment that are identified by the IPA software are ranked according to p-values. The p-values are calculated by Fisher's exact test, and can be adjusted to account for multiple testing using the methods outlined above.

10.6 ANALYSIS OF SYMPTOM BURDEN AND QUALITY OF LIFE STUDIES

The current study will examine the impact of therapy on each patient's symptom burden using the MDASI-MM tool, and about each patient's quality of life using the EORTC QLQ-C30 and QLQ-MY20 tools. Since studies using these tools in multiple myeloma patients treated with cabozantinib have not previously been performed, we are unable at this time to predict the impact of this agent on these parameters. Therefore, we hope to collect pilot data in the course of this protocol which would be hypothesis generating, and which could be confirmed in future, larger, possibly randomized trials. As a result, these studies are exploratory in nature, and their results will be examined using descriptive statistics.

10.7 REPORTING AND EXCLUSIONS

10.7.1 EVALUATION OF TOXICITY

All patients will be evaluable for toxicity from the time of their first treatment with cabozantinib.

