5.1.1 Cabozantinib

Cabozantinib tablets should be administered by mouth (PO) daily (one 20-mg capsules for the initial testing dose). Tablets should be taken with water and swallowed whole, and missed or vomited dose should not be replaced. The patient should be instructed to take the next scheduled dose at the regularly scheduled time. Patients will receive cabozantinib daily continuously during entire 28-day treatment cycle (Days 1-28 on therapy).

Refer to Section 8.2.4 for further details on administrations of other study drugs, carfilzomib and dexamethasone.

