Palmar-plantar erythrodysesthesia syndrome (PPES) occurred in 50% of patients treated with cabozantinib and was severe (Grade 3) in 13% of patients. Cabozantinib should be withheld in patients who develop intolerable Grade 2 PPES or Grade 3-4 PPES until improvement to Grade 1 when it can be resumed at a reduced dose.

Proteinuria:

Proteinuria was observed in 4 (2%) of patients receiving cabozantinib, including one with nephrotic syndrome, as compared to none of the patients receiving placebo. Urine protein should be monitored regularly during cabozantinib treatment and treatment **discontinued in patients who develop nephrotic syndrome.**

Reversible Posterior Leukoencephalopathy Syndrome:

Reversible Posterior Leukoencephalopathy Syndrome (RPLS), a syndrome of subcortical vasogenic edema diagnosed by characteristic finding on MRI, occurred in one (<1%) patient. An evaluation for RPLS should be performed in any patient presenting with seizures, headache, visual disturbances, confusion or altered mental function. **Discontinuation of cabozantinib should occur in patients who develop RPLS.**

Corrected QTc Prolongation

Cardiac arrest within 1 day of carfilzomib administration has been reported. If there is QT prolongation, we will consider holding carfilzomib.

If at any time on study there is an increase in QTcF to an absolute value > 500 ms or an increase of > 60 ms above baseline, two additional ECGs must be performed with intervals not less than 3 min apart within 30 min after the initial ECG.

If the average QTcF from the three ECGs is > 500 ms or increased by > 60 ms above baseline, the following actions must be taken:

- Interrupt study treatment
- Hospitalize symptomatic subjects (eg, with palpitations, dizziness, syncope, orthostatic hypotension, a significant ventricular arrhythmia on ECG) for a thorough cardiology evaluation and management
- Consider cardiology consultation for asymptomatic subjects for evaluation and management
- Check electrolytes, especially magnesium, potassium and calcium; correct abnormalities as clinically indicated
- Check concomitant medications for any medication that may have contributed to QT prolongation, and if possible, discontinue these medications (<http://www.qtdrugs.org>)
- Repeat ECG triplicates hourly until the average QTcF is ≤ 500 msec and the average increase is ≤ 60 ms above baseline, or otherwise determined by consultation with a cardiologist or appropriate expert.

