Cabozantinib must be taken on an empty stomach. Patients taking cabozantinib tablets should be instructed not to eat for at least 2 hours before and at least 1 hour after taking cabozantinib. Subjects should be instructed to take their cabozantinib dose at approximately the same time every day. If a subject misses a dose, the dose may be taken later only if it is within 12 hours of when the missed dose should have been taken. The missed dose should not be made up if it is within 12 hours of the next scheduled dose.

Cabozantinib tablets should be swallowed whole with at least 8 ounces of water. The tablets should be swallowed whole with water, and cannot be crushed or broken. Grapefruit, grapefruit juice, Seville oranges and their products should be avoided by subjects taking cabozantinib.

In all subjects, dose reductions and delays to manage toxicity are allowed under the guidelines in Section 5.7.

8.1.5 Potential Drug Interaction:

Cabozantinib is metabolized via a drug metabolizing enzyme system associated with cytochrome P450 (CYP3A4). Interactions with drugs metabolized via the same enzyme system are possible. Drugs which inhibit CYP3A4 may markedly increase the plasma concentration of cabozantinib.

Drugs and substances which inhibit CYP3A4 may increase the plasma concentrations of cabozantinib.

Please refer to the drug interaction tables at the following websites for lists of substrates, inducers, and inhibitors of selected CYP450 isozyme pathways:

<http://medicine.iupui.edu/flockhart/table.htm>

<http://www.fda.gov/Drugs/DevelopmentApprovalProcess/DevelopmentResources/DrugInteractionsLabeling/ucm080499.htm>

Protein Binding: Cabozantinib is highly bound ($\geq 99.7\%$) to human plasma proteins. Therefore, highly protein bound drugs should be used with caution with cabozantinib because there is a potential displacement interaction that could increase free concentrations of cabozantinib and/or a co-administered highly protein-bound drug (and a corresponding increase in pharmacologic effect).

8.1.6 Other Interactions:

Food may increase exposure levels of cabozantinib by 57%, fasting recommendations should be followed. Subjects should fast (with the exception of water) for at least 2 hours after eating the evening meal before taking their dose of cabozantinib. After the 2-hour fast and before going to bed, subjects are to take cabozantinib with a full glass of water (minimum of 8 oz or 240 mL) with no more food intake for one hour post-dose.

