In vitro data suggest that cabozantinib is unlikely to be a substrate for P-glycoprotein, but it does appear to have the potential to inhibit the P-glycoprotein transport activity. Therefore, cabozantinib may have the potential to increase plasma concentrations of co-administered substrates of P-glycoprotein.

Cabozantinib was shown to be a substrate of drug transporter MRP2 in an in vitro assay. Administration of MRP2 inhibitors to subjects may result in increases in cabozantinib plasma concentrations.

Additional details regarding potential drug interactions with cabozantinib can be found in the investigator brochure.

8.1.7 Known potential toxicities:

Cabozantinib treatment-emergent adverse events/serious adverse events of particular interest

- Gastrointestinal disorders (diarrhea, nausea and vomiting, dehydration [prostate cancer studies], stomatitis and mucositis)
- Hepatobiliary disorders (elevated ALT and AST)
- Hematological disorders
- Fatigue, anorexia, and weight loss
- Skin disorders (palmar-plantar erythrodysesthesia syndrome [PPES] and rash)

- Wound healing and surgery
- Hypertension
- Thromboembolic events (venous and arterial)
- Proteinuria
- QTc prolongation
- Hypophosphatemia
- Thyroid function disorders
- Hemorrhagic events
- Osteonecrosis of the jaw (ONJ)
- Angioedema
- Musculoskeletal and connective tissue disorders
- Respiratory, thoracic, and mediastinal disorders

8.1.8 Drug procurement:

Cabozantinib is an investigational agent supplied to investigators by Exelixis, Inc.

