An adverse event (AE) is defined as any untoward medical occurrence in a subject or clinical investigation subject administered a pharmaceutical product and which does not necessarily have a causal relationship with this treatment. An adverse event can therefore be any unfavorable and unintended sign (including an abnormal laboratory finding), symptom, or disease temporally associated with the use of a medicinal (investigational) product, whether or not the event is considered causally related to the use of the product.

An elective surgery or procedure that is scheduled to occur during a study will not be considered an adverse event if the surgery or procedure is being performed for a pre-existing condition and the surgery or procedure has been planned before study entry. However, if the pre-existing condition deteriorates unexpectedly during the study (e.g., the surgery is performed earlier than planned), then the deterioration of the condition for which the elective surgery or procedure is being done will be considered an adverse event.

An adverse event can result from use of the drug as stipulated in the protocol or labeling, as well as from accidental or intentional overdose, drug abuse, or drug withdrawal. Any worsening of a pre-existing condition or illness is considered an adverse event. Laboratory abnormalities and changes in vital signs are considered to be adverse events if they result in discontinuation from the study, necessitate therapeutic medical intervention, meet protocol specific criteria (see Section 5.0, Treatment Plan) and/or if the investigator considers them to be adverse events. In general, if a laboratory abnormality or change in vital sign is associated with a specific diagnosis that is being reported concurrently as an adverse event (e.g. elevated creatinine with renal failure or sinus tachycardia in febrile neutropenia) the findings that support the diagnosis do not need to be reported as separate adverse events unless the investigator feels it is appropriate.

Treatment-emergent Adverse Event

Treatment-emergent adverse event is defined as any adverse event with onset or worsening from the time that the first dose of study drug is administered until 30 days after the final dose of study drug is administered.

Unexpected Adverse Event

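### Toxicity evaluability and replacement are tied to cabozantinib alone, so a patient given carfilzomib or dexamethasone but never cabozantinib has no consistent place in the toxicity, 3+3 or ORR counts

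*Combined protocol and SAP*

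**What the plan says.** **The two rules.** Section 10.7.1 contains one sentence: "All patients will be evaluable for toxicity from the time of their first treatment with cabozantinib". Section 10.7.2 adds: "Those patients who do not receive a single dose of the investigational drug will be replaced in this trial with new patients". Section 8.1.8 shows which drug that means: "Cabozantinib is an investigational agent supplied to investigators by Exelixis, Inc". Section 8.2.3 describes carfilzomib as commercially available.

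**The regimen.** The schema puts all three drugs on day 1. Section 5.1.1 treats the other two as study drugs: "Refer to Section 8.2.4 for further details on administrations of other study drugs, carfilzomib and dexamethasone".

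**Other text on the same question.**
- Section 9 follows toxicity from consent, and 9.1.2 collects adverse events from signature of the consent form.
- Section 9 defines a treatment-emergent event as "any adverse event with onset or worsening from the time that the first dose of study drug is administered", up to 30 days after the last dose.
- Sections 5.7 and 10.1 base DLTs on adverse events in cycle 1 and do not mention the first cabozantinib dose.
- Section 10.2 tabulates all observed toxicities by type and grade.
- Section 6.2 defines the response rates on an intent-to-treat basis.
- Section 10.7.2 keeps all eligible patients in the main response analysis, "with the possible exception of those who received no study medication". It also counts early death from toxicity as treatment failure.

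**Timing of cabozantinib.** Section 8.1.6 says: "After the 2-hour fast and before going to bed, subjects are to take cabozantinib". Section 8.1.4 asks only for about the same time each day, and has three additional patients start cabozantinib 1-2 days before carfilzomib.

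**The concern.** The trial evaluates a combination, but the analysis section starts the clock for toxicity, and decides who is replaced, by one component. A patient can receive the day 1 carfilzomib infusion, have a serious reaction, and stop before any cabozantinib. That patient has received protocol treatment and may have had a DLT.

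The plan gives no single answer on whether this patient is in the toxicity denominator, counts in the 3+3 cohort, or is a non-responder in the ORR. With cohorts of three to six and a final response decision on 17 patients, one patient can change a decision. The literal rules resolve each question in the regimen's favour: a toxicity is left out of a denominator, a DLT is swapped for a fresh patient, or a treatment failure is swapped for someone who may respond.

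**Working it through.** The plan states no figure on this point, so the check is mainly a comparison of texts. The test case is a patient who received carfilzomib (with or without dexamethasone) and never took cabozantinib.

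**1. Toxicity population.** Under 10.7.1 evaluability never begins. Under section 9 the patient is followed from consent, and any event after the infusion is treatment-emergent because carfilzomib is a study drug (5.1.1). Under 10.2 the event is tabulated. The event is therefore recorded, but whether the patient belongs in the denominator is contradictory.

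**2. DLT count.** Under 5.7 and 10.1 a qualifying cycle 1 event is a DLT. Under 10.7.2 the patient is replaced. Nothing says whether the DLT stays with the cohort.

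**3. ORR.** The exception in 10.7.2 covers only patients with no study medication. This patient had some, so stays in the main analysis, as 6.2 also implies. The replacement sentence, which follows directly, uses the other term and replaces the same patient. Whether the ORR then counts the original patient, the replacement or both is not stated. At the boundary this matters: section 10.1 rejects the drug at 2 or fewer responses in 17. If 16 patients give 2 responses and the 17th is the test case, the result is 2/17 (reject). If a replacement takes that place and responds, it is 3/17 (do not reject).

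**4. Possible effect on escalation (illustration only).** Let p be the true cycle 1 DLT rate. Let q be the part of p made up of DLTs before cabozantinib in patients who then never take it. The documents give no value for q, so the values below are assumptions. The usual 3+3 rule is also assumed: escalate on 0 of 3, or on 1 of 3 followed by 0 of 3.

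- P(escalate) = (1 − p)³ + 3p(1 − p)² × (1 − p)³.
- If the q patients are replaced and not counted, p becomes (p − q)/(1 − q).
- At p = 0.30 with everyone counted: 0.343 + 0.151 = 0.494.
- At p = 0.30 and q = 0.02: (0.30 − 0.02)/0.98 = 0.286, which gives 0.364 + 0.159 = 0.524 (from unrounded values).

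| True DLT rate p | All counted | q = 0.02 | q = 0.05 | q = 0.10 |
|---|---|---|---|---|
| 0.20 | 0.709 | 0.744 | 0.798 | 0.887 |
| 0.30 | 0.494 | 0.524 | 0.572 | 0.660 |
| 0.40 | 0.309 | 0.330 | 0.363 | 0.428 |

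Every shift is toward escalation: 2 to 4 percentage points at q = 0.02, and 12 to 18 points at q = 0.10. The larger values of q look high for patients whom inclusion criterion 4 requires to have tolerated carfilzomib well.

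**The case against.** The strongest reply is that 10.7.1 takes nothing out of the safety data. Events are collected from consent, treatment-emergent events run from the first study drug, DLTs cover all of cycle 1, all observed toxicities are tabulated, and events of grade 3 or above go to the safety committee whatever their attribution (9.1.2). This stands. A reader might infer that day 1 toxicity as a whole falls outside the safety evaluation; the documents do not support that. For a patient who takes cabozantinib later that day, the gap is a matter of hours and the events are still recorded.

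Three further inferences are tempting and go too far.
- *Replaced patients are deleted from the ORR.* Section 10.7.2 does not say so. Replacing can simply mean enrolling one more patient, and the replacement sentence can be read as referring back to patients with no study medication. The denominator is contradictory, not demonstrably shrunk.
- *Most patients receive carfilzomib hours before cabozantinib.* Bedtime dosing appears only in 8.1.6, no hour is set for the infusion, and the order is reversed for the three additional patients. The inconsistency does not need this premise: it arises whenever another study drug comes first and cabozantinib is never taken.
- *The listed toxicity rates measure the problem.* Section 8.2.2 lists infusion reaction as affecting more than 1 in 10 patients, which would be about 0.10 × 29 = 2.9 of 29. That frequency is not tied to a grade or to the first infusion, and it does not count patients who never take cabozantinib. Section 5.7.1 notes: "Cardiac arrest within 1 day of carfilzomib administration has been reported". That does not place the event before the first cabozantinib dose.

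**Conclusion.** The point holds as a contradiction between rules, with a narrow reach. Sections 10.7.1 and 10.7.2 use cabozantinib as the anchor where sections 5.7, 6.2, 9, 10.1 and 10.2, and another sentence of 10.7.2, do not. Only a patient who receives carfilzomib or dexamethasone but never cabozantinib is affected. For that patient the toxicity and ORR denominators are contradictory and the 3+3 count is undefined.

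Such patients should be rare, and the documents give no rate, so no size can be claimed beyond a labelled assumption. If 1% to 3% of patients were affected, the chance of at least one among 29 would be 1 − 0.99²⁹ = 0.25 to 1 − 0.97²⁹ = 0.59. The escalation figures are likewise conditional on an assumed q and on the usual 3+3 rule. What does not depend on these assumptions is the direction: excluding such a DLT or treatment failure favours the regimen. The rule should be settled before analysis so that the denominator is not chosen after the event is known.

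**What to change.** - **10.7.1:** state that every patient enters the toxicity population at the first dose of any protocol drug (carfilzomib, dexamethasone or cabozantinib).
- **10.7.2:** use one term, study medication, defined as any protocol drug, for both exclusion and replacement. Only patients who received none are replaced. Any eligible treated patient in the phase II analysis stays in the ORR denominator, as a non-responder if no response is documented.
- **3+3 count (10.1 or 10.2):** a patient with an event meeting the cycle 1 DLT definition counts in the cohort even if no cabozantinib was taken. A phase I patient with no cabozantinib and no DLT may be replaced for the 3+3 count only, and is still reported in the toxicity table. Without the first of these sentences, a replacement rule could discard a DLT.
- **8.1.4 and 8.1.6:** the sponsor should reconcile the statements on when cabozantinib is taken relative to carfilzomib. This is a request for consistency, not a view on which timing is right.

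The statistical changes amount to a few sentences, with no new data and no change to the planned sample size. The cost is a possibly slightly lower ORR or slightly higher toxicity rate.
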